11.2 SAMPLE SIZE DETERMINATION

As this is a first in human study of a medical device a statistically determined sample size was not used. Rather, the subject number of eight was chosen as it is consistent with the FDA's recommended number of 6-10 subjects for a first in human study of a medical device.

The anticipated dropout rate after subjects have begun closed loop glucose control is less than 10%, which should not significantly affect the study results. No interim analysis is planned. Given the small sample size no subgroup analysis is planned.

11.3 POPULATIONS FOR ANALYSES

Not applicable. All subjects who begin closed loop glucose control will be used for analysis.

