9 STUDY INTERVENTION DISCONTINUATION AND PARTICIPANT DISCONTINUATION/WITHDRAWAL

9.1 DISCONTINUATION OF STUDY INTERVENTION ON INDIVIDUAL SUBJECT

In the context of this study, termination is defined as the act of bringing either the study on one subject, or the entire study to a permanent end.

On each subject the study will be immediately terminated for any of the following reasons:

A. Termination Criteria for individual subjects:

The study will be terminated on individual subjects if any of the following criteria are met:

1. Subject or their legal authorized representative requests withdrawal from the study for any reason.
2. The clinical study nurses are unable to insert two working Dexcom G6 CGM's prior to beginning the closed loop glucose control session.
3. Subject has a Reference Glucose Value less than 54 mg/dL.
4. Subject has signs of prolonged severe hyperglycemia, as defined by Reference Glucose Value > 240 mg/dL for more than 2 hours.
5. Subject has signs of DKA, as defined by a Reference Glucose Value > 240 mg/dL and blood ketones > 1 mmol/L.
6. CGM or Reference Glucose Value remains > 300 mg/dL for more than 1 hour.
7. FUSION system has only one Dexcom G6 CGM available for use for more than 4 hours.
8. FUSION system has no Dexcom G6 CGM's available for use for more than 20 minutes.
9. There are no Reference Glucose Values for a period of time greater than 60 minutes.
10. The FUSION system experiences any unanticipated adverse device effect (UADE).
11. The subject has had more than 2% of their estimated total blood volume drawn during visit 3.
12. The FUSION system delivers more than 2000 mL (insulin and dextrose infusions) during the 24-hour closed loop glucose control session.

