9.2 DISCONTINUATION OF ENTIRE STUDY

A. Termination Criteria for the entire study:

The entire study will be terminated if any of the following criteria are met:

1. Two subjects experience an episode of severe hypoglycemia (Reference Glucose Value < 54 mg/dL) during the time period the FUSION system is in use.
2. Two subjects experience an episode of severe hyperglycemia, as defined by a Reference Glucose Value > 240 mg/dL for more than 2 hours.
3. One subject experiences an episode of DKA after starting the closed loop glucose control session.
4. One subject experiences an episode of HHS after starting the closed loop glucose control session.
5. The FUSION system delivers more than 2000 mL (insulin and dextrose infusions) during the 24-hour closed loop glucose control session in two subjects.
6. The FUSION system experiences any unanticipated adverse device effect (UADE).
7. The study's principal investigator determines that the safety of the studies subjects is being compromised through use of the FUSION system.

If subjects are removed from the study due to hypoglycemia or the development of diabetic ketoacidosis, they will have ongoing monitoring and care in the CRC as noted in [Recovery Period](#) (pages 107-108). If a subject signs an informed consent but does not receive closed loop glucose control, they may be replaced. If a subject begins the closed loop glucose control portion of the study, they may not be replaced.

If the study has been terminated on only one subject for a reason other than an unanticipated adverse device effect, the study may continue. If the entire study has been terminated, it may not be resumed until the study's sponsor has submitted study results to the FDA, the study sponsor has presented plans to mitigate the risks that led to the study's termination, and the FDA has approved resumption of the study.

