10.3.4 TIME PERIOD AND FREQUENCY FOR EVENT ASSESSMENT AND FOLLOW-UP

The occurrence of an adverse event (AE) or severe adverse event (SAE) may come to the attention of study personnel during study visits or upon review by a study monitor.

All Aes including local and systemic reactions not meeting the criteria for SAEs will be captured on the appropriate case report CRF. Information to be collected includes event description, time of onset, clinician's assessment of severity, relationship to medical device under study (assessed only by those

DEMONSTRATION OF AN ARTIFICIAL INTELLIGENCE BASED CLOSED LOOP GLUCOSE CONTROL SYSTEM AS A THERAPEUTIC MODALITY IN TYPE 1 AND TYPE 2 DIABETIC PATIENTS

Protocol IMT 2022-1

CONFIDENTIAL

Version1.0.7

22 August 2022

with the training and authority to make a diagnosis), and time of resolution/stabilization of the event. All Aes occurring while on study must be documented appropriately regardless of relationship. All Aes will be followed to adequate resolution.

Any medical condition that is present at the time that the participant is screened will be considered as baseline and not reported as an AE. However, if the study participant's condition deteriorates at any time during the study, it will be recorded as an AE.

Changes in the severity of an AE will be documented to allow an assessment of the duration of the event at each level of severity to be performed. Aes characterized as intermittent require documentation of onset and duration of each episode.

The Principal Investigator or his designee will record all reportable events with start dates occurring any time after informed consent is obtained until 1 (for non-serious Aes) or 3 days (for SAEs) after the last day of study participation. At each study visit, the investigator will inquire about the occurrence of AE/SAEs since the last visit. Events will be followed for outcome information until resolution or stabilization.

Unsolicited adverse events are not applicable to this study.

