11.4.4 SAFETY ANALYSES

For the safety primary endpoint of percent time in range < 70 mg/dL, the calculation is as follows:

(# of glucose values in range < 70 mg/dL/total number of all glucose values) * 100

This result will be presented as median and interquartile range (25-75).

Each AE or SAE will be independently reported as percent of patients experiencing the event. SAE's that require stopping the study prematurely will be separately reported in a table. If the principal investigator feels the AE or SAE's are secondary to the intervention this will be reported in the final study summary. Any rescue medicine that is used per 8.5.1 will be separately reported as percent of subjects requiring rescue medicine.

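### No safety set covers subjects who undergo study procedures but never start closed loop, so the planned adverse event percentages and start-failure counts leave them out

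*Combined protocol and SAP*

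**What the plan says.** Section 11.3 (Populations for Analyses) is marked not applicable and then gives one rule: "All subjects who begin closed loop glucose control will be used for analysis". It defines no safety population.

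On replacement, section 9.2 says "If a subject signs an informed consent but does not receive closed loop glucose control, they may be replaced" and, for starters, "If a subject begins the closed loop glucose control portion of the study, they may not be replaced". Section 9.3 repeats both rules.

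Section 9.1, item 2, makes the following a reason to end the study on an individual: "The clinical study nurses are unable to insert two working Dexcom G6 CGM's prior to beginning the closed loop glucose control session".

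Recording begins earlier. Under section 10.3.4 the investigator "will record all reportable events with start dates occurring any time after informed consent is obtained". The Schema (1.2) treats CGM placement on arrival at visit 3 as the first administration of the study intervention. The Schedule of Activities (1.3) marks both study intervention and adverse event review at visit 3, time 0 to 5 hours.

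For reporting, section 11.4.4 says "Each AE or SAE will be independently reported as percent of patients experiencing the event". It names no denominator. Serious events that stop the study early get a separate table. Section 11.4.8 marks tabulation of individual data as not applicable.

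**The concern.** Exposure and recording start before the session, while the only analysis set starts with it. A subject can change medicines on study instruction, receive insulin in the research center, have lines and sensors placed, have an adverse event or a sensor failure, and then be replaced. If section 11.3 supplies the missing denominator for section 11.4.4, that subject appears in no adverse event percentage.

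The CGM case matters most. The two CGMs are a listed component of the FUSION system, and being unable to start because they do not work is a feasibility finding in an early feasibility study. Replacing such subjects without counting them makes both safety and start success look better than what was observed. With eight subjects, one omitted person is visible in any percentage.

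**Working it through.** **1. The plan's own figure.** The sample is 2 type 1 + 6 type 2 = 8, which agrees with section 11.2. It was chosen to fit a recommended range, so there is no formula to reproduce. Section 11.2 gives an anticipated dropout (below 10%) only for the period after closed loop has begun. No pre-session rate is given anywhere.

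**2. What happens before the session.**

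| Time | Study-ordered step | Source |
|---|---|---|
| Days before visit 3 | Some oral agents stopped or withheld; some evening insulin doses changed | 8.1.1.3 |
| 0 to 1 h | Glucose check and, if triggered, ketone screen; ketones above 1 mmol/L cancel the study | 8.1.1.4 step 2; Protocol 2 item 7 |
| After that screen | Two CGMs and two IV lines placed | 8.1.1.4 steps 3 and 4 |
| About 1 h | Breakfast with investigator-determined short acting insulin | Protocol 2 items 8 and 9 |
| Up to 5 h | CGM validation; the session may not begin without two working CGMs | Protocol 2 item 16; 9.1 item 2 |

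Two exits follow from this order:

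- *Ketone cancellation* comes before instrumentation and before the breakfast insulin. Its only relevant prior exposure is the medication change, where one was ordered.
- *CGM start failure* would normally be declared after breakfast insulin, lines and sensors, because validation runs toward a start at about 1200 and breakfast is at about 0800.

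**3. Whether a planned result catches them.** The endpoints in 11.1 and the analyses in 11.4.2 to 11.4.4 contain no count of start failures or replacements. Ketosis that cancels a session need not be a serious event: cancellation occurs above 1 mmol/L, while the DKA entry in 10.3.3.1 requires symptoms, ketones above 1.5 mmol/L and acidosis criteria. Likewise, an uncomplicated glucose of 54-69 mg/dL after the breakfast insulin does not meet the below-54 mg/dL entry in that list.

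**4. Effect of the denominator (assumption-based illustration).** Assume no events in the 8 starters, k replaced non-starters, and one event in each non-starter.

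- Starters only: 0/8.
- All admitted to visit 3: k/(8 + k).
- Intervals are exact (Clopper-Pearson) 95%.

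| k | Starters only | All admitted | 95% interval, all admitted |
|---|---|---|---|
| 1 | 0/8 = 0% | 1/9 = 11.1% | 0.3 to 48.2% |
| 2 | 0/8 = 0% | 2/10 = 20.0% | 2.5 to 55.6% |
| 3 | 0/8 = 0% | 3/11 = 27.3% | 6.0 to 61.0% |

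The interval for 0/8 is 0 to 36.9%. The intervals overlap widely. The change is in what is reported, not in what eight subjects can establish.

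**5. How likely a non-starter is.** Let p be the chance that an admitted subject does not start. The chance of at least one among the first 8 admitted is 1 − (1 − p)^8. The expected number before 8 starters are reached is 8p/(1 − p).

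| Assumed p | At least one in 8 | Expected non-starters |
|---|---|---|
| 5% | 34% | 0.4 |
| 10% | 57% | 0.9 |
| 20% | 83% | 2.0 |

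**The case against.** Several points on the other side stand.

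- **The information is kept.** A reader might infer that these events are lost. The documents do not support that. Section 10.3.4 says adverse events "occurring while on study must be documented appropriately regardless of relationship". Section 7.4 requires screen failure details and any serious event. Section 9.3 puts the reason for removal on the case report form. Section 10.3.8 sends study-preventing device malfunctions to the sponsor, IRB and regulators, and the Independent Safety Monitor (12.1.6) reviews adverse events and cumulative data. However, none of these is a planned summary in the results. Section 7.4 also does not say whether someone who fails to start at visit 3 is a screen failure.
- **The exclusion is an inference.** Section 11.3 speaks of all who begin, not only those who begin, and 11.4.4 does not cite it. If the sponsor means something wider, the denominator is simply undefined and the same edit is needed.
- **The 16-to-8 step in the Schema.** A reader might infer that up to half of consented subjects fall outside the analysis set after exposure. That is not supported. The 16 are subjects at visit 2, where laboratory results and eligibility decide who proceeds; the Schema plans 8 at visit 3. The gap is mainly planned screening attrition before any visit 3 procedure.
- **The ketone case.** A reader might infer that a subject cancelled for ketones had already been dosed and instrumented. The order of steps shows otherwise.
- **The glycemic endpoints.** Their time frame is controller use, so starters are the right set for them, including for the primary safety endpoint.

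**Conclusion.** The concern holds as a gap in the planned safety results. Read together, 11.3 and 11.4.4 leave non-starters out of the adverse event percentages, and nothing planned counts subjects who could not start for want of two working CGMs. It does not amount to lost safety data, and it does not touch the glycemic endpoints.

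No size can be taken from the documents, because they give no pre-session non-start rate. Under the stated assumption of no events in eight starters, one event in one replaced subject changes 0% to 11.1%, and two in two change it to 20%. The conclusion rests on 11.3 supplying the denominator for 11.4.4, which is the natural reading but is not stated. It is a cheap improvement worth making.

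**What to change.** 1. In 11.3, keep subjects who begin closed loop as the set for glycemic endpoints. Add a safety set of all consented subjects who had any study-ordered medication change or any visit 3 procedure.
2. In 11.4.4, report adverse events on the safety set by phase (before, during and after FUSION), with the denominator given for each phase.
3. In 11.4.4, report the number of visit 3 admissions that did not start and the number replaced, by reason, with CGM start failure as its own category.
4. In 7.4, state whether a subject who reaches visit 3 but does not start counts as a screen failure.

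The cost is a few sentences and one extra table from data already recorded. The reported safety and start-success figures may look slightly less favorable.

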11.4 STATISTICAL ANALYSES

11.4.1 GENERAL APPROACH

The data will be presented as median and interquartile range (25-75), except for the Clarke error grid analysis which will be presented as percent of values in zones A, B, C, D and E.

11.4.2 ANALYSIS OF THE PRIMARY EFFICACY ENDPOINT(S)

1. To determine percent time in range < 70 mg/dL for each subject, the calculation is as follows:

(# of glucose values in range < 70 mg/dL/total number of all glucose values) * 100

This result will be presented as median and interquartile range (25-75).

2. To determine percent time in range 70-180 mg/dL for each subject, the calculation is as follows:

(# of glucose values in range 70-180 mg/dL/total number of all glucose values) * 100

This result will be presented as median and interquartile range (25-75).

11.4.3 ANALYSIS OF THE SECONDARY ENDPOINT(S)

For the secondary endpoints that measure percent time in range, the values will be calculated as noted above in 9.4.2. These results will be presented as median and interquartile range (25-75).

The number of hypoglycemic events less than 70 mg/dL will be presented as median and interquartile range (25-75).

The mean glucose level will be presented as mean \pm SD.

The coefficient of variation will be presented as median and interquartile range (25-75).

The Clarke error grid analysis will be presented as a graph of the Clarke error grid. The Reference Glucose Value (Nova StatStrip Hospital Glucose Meter System) and Dexcom G6 data will be analyzed to determine the percent of all values that are in zones A, B, C, D and E.

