2. The primary efficacy endpoint will be the percent of all glucose values that are within the glucose range of 70-180 mg/dL.

DEMONSTRATION OF AN ARTIFICIAL INTELLIGENCE BASED CLOSED LOOP GLUCOSE CONTROL SYSTEM AS A THERAPEUTIC MODALITY IN TYPE 1 AND TYPE 2 DIABETIC PATIENTS

Protocol IMT 2022-1

CONFIDENTIAL

Version1.0.7

22 August 2022

Time frame will be from start of use of AI controller until end of use of AI controller.

Secondary Endpoints:

- Measure the percent of glucose values that are within clinically significant hypoglycemic range (glucose <54 mg/dL).
- Measure the percent of glucose values that are within the moderate hypoglycemic range of 54-69 mg/dL.
- Number of hypoglycemic events as measured by glucose < 70 mg/dL.
- Measure the percent of glucose values that are within the desired glucose control range of 100-140 mg/dL.
- Measure the percent of glucose values that are within the range of 70-140 mg/dL.
- Measure the percent of glucose values that are within the hyperglycemic range of >140 mg/dL.
- Measure the percent of glucose values that are within the range of 70-180 mg/dL.
- Measure the percent of glucose values that are within the hyperglycemic range of >180 mg/dL.
- Mean glucose level.
- Measure of dispersion – coefficient of variation (CV).
- The study data will be used to determine the percentage of paired glucose values (continuous glucose monitor(s) and Reference Glucose Value) in each zone using a Clarke error grid analysis.¹ These calculations will be performed for each individual CGM system and for the glucose value used by the FUSION system for purposes of glucose control (a calculated average of the two CGM systems).

Time frame will be from start of the use of AI controller until end of use of AI controller.

Study Population: Two participants with type 1 diabetes and six participants with type 2 diabetes, male and non-pregnant females, ages 18-70 inclusive, admitted to a CRC. Participants will eat three standardized meals during their 24-hour closed loop glucose control study.

DEMONSTRATION OF AN ARTIFICIAL INTELLIGENCE BASED CLOSED LOOP GLUCOSE CONTROL SYSTEM AS A THERAPEUTIC MODALITY IN TYPE 1 AND TYPE 2 DIABETIC PATIENTS

Protocol IMT 2022-1

CONFIDENTIAL

Version1.0.7

22 August 2022

Phase: Early Feasibility Study, First in Human.

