| The secondary objectives of the study are to assess the controller's ability to minimize glucose curve measurements associated with increased ICU morbidity/mortality rates, and to maximize those measurements associated with decreased ICU morbidity/mortality rates. | 
 1. Measure the percent of glucose values that are within the severe hypoglycemic range of 0 – < 54 mg/dL. 2. Measure the percent of glucose values that are within the moderate hypoglycemic range of 54-69 mg/dL. 3. Number of hypoglycemic (< 70 mg/dL) events. Each event separated by at least one glucose value ≥ 70 mg/dL. 4. Measure the percent of all glucose values that are within the desired glucose control range of 100 – 140 mg/dL. 5. Measure the percent of glucose values that are within the range of 70-140 mg/dL. 6. Measure the percent of glucose values that are within the hyperglycemic range of > 140 mg/dL. 7. Measure the percent of glucose values that are within the range of 70-180 mg/dL. 8. Measure the percent of glucose values that are within the hyperglycemic range of > 180 mg/dL. 9. Mean glucose level (mg/dL). 10. Measure of dispersion – coefficient of variation. 11. The study data will be used to determine the percentage of the Dexcom's G6 CGM's glucose values in each zone using a Clarke error grid analysis.¹ This same calculation will be performed on the average of the two Dexcom | The chosen secondary endpoints are routinely measured in glucose control studies and serve to provide a more complete picture of the AI based glucose control systems ability to both safely and effectively provide glucose control. |

DEMONSTRATION OF AN ARTIFICIAL INTELLIGENCE BASED CLOSED LOOP GLUCOSE CONTROL SYSTEM AS A THERAPEUTIC MODALITY IN TYPE 1 AND TYPE 2 DIABETIC PATIENTS

Protocol IMT 2022-1

CONFIDENTIAL

Version1.0.7

22 August 2022

| OBJECTIVES | ENDPOINTS | JUSTIFICATION FOR ENDPOINTS |
|----------------------|---|-----------------------------|
| | G6 CGM systems used by the FUSION system for purposes of glucose control. | |
| Tertiary/Exploratory | | |
| None planned | | |

The glucose data for the above statistical analysis will be the glucose data used by the FUSION system for purposes of glucose control, unless otherwise specified.

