8.1.1.5 VISIT 3, TIME 5 TO 29 HOURS (CLOSED LOOP GLUCOSE CONTROL SESSION)

The closed loop glucose control session will not begin until the following criteria has been met:

1. Both Dexcom G6 CGM's are returning glucose values and have been calibrated – if necessary; or replaced – if necessary.

Please refer to the below standard operating procedure (SOP) document for the calibration procedure for the Dexcom G6 CGM's, setting up the FUSION system, and initiating it's software:

FUSION System SOP

To better simulate how the FUSION system will be used in the ICU setting, no run-in period will be performed prior to the subject consuming the first meal. During the 24-hour closed loop glucose control study (time 5 to 29 hours), blood glucose control will be performed autonomously by Ideal Medical Technologies FUSION glucose control system. For safety reasons, the subjects will have a Reference Glucose Value independently measured every 10-60 minutes on the Nova StatStrip Hospital Glucose Meter System. These independent Reference Glucose Values will not be used by the FUSION system for glucose control. After 2-3 hours of confirmed CGM accuracy (e.g., from 0900 to 1200), the closed loop glucose control session will begin. The first meal consumed during the closed loop glucose control session will be lunch.

Lunch will consist of 60 grams of carbohydrate (45-60% of total meal Kcal's) and be consumed beginning at ~1200 hours (the beginning of the closed loop glucose control session). Dinner will consist of 75 grams of carbohydrates (45-60% of total meal Kcal's) and be consumed beginning at 1800 hours (6 hours after beginning of closed loop glucose control session). Breakfast will consist of 50 grams of carbohydrate (45-60% of total meal Kcal's) and be consumed beginning at 0800 hours on day 2 of the closed loop session began (20 hours after the beginning of the closed loop glucose control session).

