11.1 STATISTICAL MEASUREMENTS

Primary Safety and Efficacy Endpoints:

1. Safety

The safety of the FUSION system will be determined by its ability to avoid hypoglycemia in adult type 1 and type 2 diabetic patients consuming three meals over a period of 24 hours. Safety will be measured by calculating the percent of all glucose values that are within the hypoglycemic range of less than 70 mg/dL.

Statistics – No statistical comparison will be made for this measurement.

2. Efficacy

The efficacy of the FUSION system will be determined by its ability to maintain glucose in the normal range in adult type 1 and type 2 diabetic patients consuming three meals over a period of 24 hours. Efficacy will be measured by calculating the percent of all glucose values that are within the normal glucose range of 70-180 mg/dL.

Statistics – No statistical comparison will be made for this measurement.

Secondary Efficacy Endpoints:

The secondary objectives of the study are to assess the controller's ability to minimize glucose curve measurements associated with increased ICU morbidity/mortality rates, and to maximize those measurements associated with decreased ICU morbidity/mortality rates.

1. Measure the percent of glucose values that are within the severe hypoglycemic range of 0- <54 mg/dL.

Statistics – No statistical comparison will be made for this measurement.

2. Measure the percent of glucose values that are within the moderate hypoglycemic range of 54-69 mg/dL.

Statistics – No statistical comparison will be made for this measurement.

3. Measure the number of hypoglycemic (< 70 mg/dL) events.

Statistics – No statistical comparison will be made for this measurement.

DEMONSTRATION OF AN ARTIFICIAL INTELLIGENCE BASED CLOSED LOOP GLUCOSE CONTROL SYSTEM AS A THERAPEUTIC MODALITY IN TYPE 1 AND TYPE 2 DIABETIC PATIENTS

Protocol IMT 2022-1

CONFIDENTIAL

Version1.0.7

22 August 2022

4. Measure the percent of all glucose values that are within the desired glucose control range of 100-140 mg/dL.

Statistics – No statistical comparison will be made for this measurement.

5. Measure the percent of glucose values that are within the range of 70-140 mg/dL.

Statistics – No statistical comparison will be made for this measurement.

6. Measure the percent of glucose values that are within the hyperglycemic range of > 140 mg/dL.

Statistics – No statistical comparison will be made for this measurement.

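### The hypoglycemic event endpoint is a raw count per subject with no hours beside it, although stopping rules can shorten sessions, so it can understate event frequency; the effect is modest.

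*Combined protocol and SAP*

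**What the plan says.** Section 5 lists the number of events below 70 mg/dL as a secondary endpoint and defines how events are separated: "Each event separated by at least one glucose value ≥ 70 mg/dL". Section 11.1 repeats it as "Measure the number of hypoglycemic (< 70 mg/dL) events", and section 11.4.3 gives the summary: "The number of hypoglycemic events less than 70 mg/dL will be presented as median and interquartile range (25-75"). None of these places mentions time at risk. The percent endpoints in sections 11.4.2 and 11.4.4 do divide, by the subject's total number of glucose values.

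The window is the period of controller use (section 1.1): "Time frame will be from start of the use of AI controller until end of use of AI controller". Section 8.1.1.5 plans 24 hours, but section 9.1 lists twelve reasons to terminate a subject. One is "Subject has a Reference Glucose Value less than 54 mg/dL". Others concern prolonged high glucose, loss of CGM data and infused volume.

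Sections 9.2 and 9.3 do not allow a subject who has begun closed loop to be replaced, and section 11.3 says "All subjects who begin closed loop glucose control will be used for analysis". Section 11.4.8 marks tabulation of individual data as not applicable.

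**The concern.** A count means the same thing across subjects only if they are watched for the same time. Here they need not be, and one reason for a short session is low glucose, the condition being counted. One event before a stop at 4 hours and one event in a full session are both recorded as 1.

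This is the only endpoint that counts hypoglycemic episodes. No rule covers counts from shortened sessions, and the plan does not commit to showing which counts came from them. A reader of the median and IQR could not tell a low count over 24 hours from a low count over a few hours.

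**Working it through.** The plan gives no event rate, so there is no figure of its own to reproduce. Event rates, stop times and the chance that an event leads to a stop are assumptions below.

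**1. Direction.** Stopping a session can only remove later events. The observed count is therefore at most the count the same subject would have had over 24 hours. This needs no model.

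**2. One subject.** Rate per 24 h = count × 24 / hours. One event before a stop at 2, 4, 6, 12 or 23 h is a count of 1 each time, but a rate of 12.0, 6.0, 4.0, 2.0 or 1.04. The loss depends on when the stop occurs and is trivial near the end.

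**3. Eight subjects, assumed data.** Two stop at 4 h and 6 h with one event each; six complete with 2, 2, 2, 2, 3, 3.
- Counts: median 2.0 (IQR 1.75–2.25), with the stopped subjects lowest.
- Rates per 24 h (6, 4, 2, 2, 2, 2, 3, 3): median 2.5 (IQR 2.0–3.25), with the stopped subjects highest.
- Pooled: 16 events over 4 + 6 + 6 × 24 = 154 h, so 16 / 154 × 24 = 2.49 per 24 h, against a mean count of 16 / 8 = 2.0.

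If instead the six completers have no events, the stopped subjects rank highest on both scales and both medians are 0. The pooled rate is 2 / 154 × 24 = 0.31, against a mean count of 0.25.

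**4. Average size.** Let events occur at a constant rate L per 24 h, and let each independently stop the session with probability p.
- Share of subjects stopped = 1 − exp(−Lp).
- Mean fraction of the session observed = (1 − exp(−Lp)) / (Lp).
- Two of eight stopped: 1 − exp(−Lp) = 0.25, so Lp = −ln(0.75) = 0.288.
- Fraction observed = 0.25 / 0.288 = 0.87, a shortfall of about 13%.

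The result depends only on the product Lp. If the second such stop came before the eighth subject, the stopped share would exceed 25%, but the study would already have ended for safety.

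**5. Ranking.** Simulation under the same model, with p from 0.10 to 0.25, gave stopped subjects about 10–12 h of exposure and these mean observed counts:

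| Events per 24 h (assumed) | Stopped | Completers |
|---|---|---|
| 1 | 1.4 | 0.8–0.9 |
| 2 | 1.7–1.9 | 1.5–1.8 |
| 4 | 2.3–2.7 | 3.0–3.6 |

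Stopped subjects fall below completers on average only when events are frequent.

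**6. Two measurements.** The stop uses the Reference value. The count uses the glucose data on which FUSION acts (section 11.1), which is the average of two CGMs. A Reference value of 50–53 mg/dL with a CGM average of 70–73 mg/dL is within the 20 mg/dL validation tolerance of section 8.1.1.4. Such a session could end with a count of zero, and a rate would also be zero.

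**The case against.** The strongest reply is that little rests on this endpoint and that the serious cases are reported elsewhere. It is one of eleven descriptive secondary endpoints in a study of eight, with no comparison and no hypotheses. A Reference value below 54 mg/dL is a severe adverse event under section 10.3.3.1. Section 11.4.4 reports adverse events as percent of patients and puts serious events that stop the study early in a separate table. Percent of values below 54 and below 70 mg/dL are endpoints too. All of this stands and limits the severity, but none of it gives an episode frequency.

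The documents also give some reason to expect few events. Section 4.1 reports no time below 70 mg/dL in the two earlier human subjects, and section 11.2 expects dropout under 10%, which is less than one of eight (0.8). That is thin evidence, but it means the bias may be nil in practice.

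A reader might infer a much larger understatement. In the model above, L = 4 with p = 0.25 gives a 37% shortfall, and L = 8 with p = 0.5 gives 75%. Those settings imply that 63% and 98% of subjects stop for a value below 54 mg/dL. Section 9.2 ends the study at two such subjects, so these sizes do not fit a study that treats all eight.

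A reader might also infer that the worst-affected subjects will show the lowest counts, or that every rule in 9.1 shortens sessions. Neither follows. The ranking reverses only against completers with several events, and the rule on failing to place two working CGMs applies before the session begins.

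**Conclusion.** The point holds in a limited form. Followed as written, section 11.4.3 can understate event frequency when a session is cut short, and nothing else in the plan adjusts for this. With two of eight subjects stopped for a value below 54 mg/dL, the mean shortfall is about 13%, assuming a constant event rate and an independent chance that each event stops the session. It is larger if other stops also shorten sessions, and zero if none does. The documents do not support the stronger reading that the device will necessarily look safer than it is. This is a reporting improvement worth making; it does not undermine the study's primary results.

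**What to change.** In section 11.4.3, keep the per-subject count with its median and IQR, and add two items:

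- a listing of each subject's event count beside closed-loop hours (start to end of controller use) and the reason for any early stop;
- the pooled rate: total events / total closed-loop hours × 24.

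Section 11.4.8 should then refer to this listing instead of saying not applicable. The cost is a sentence or two and a division; the FUSION display described in section 3 already shows elapsed time. No stopping rule changes.

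The pooled rate assumes roughly constant risk across a session that contains three meals and a night. Per-subject rates from very short sessions are unstable and should not be summarised alone. The rate does not resolve the CGM–Reference mismatch, which is why the reason for stopping belongs beside the count.
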